15.4.1. Efficacy Analyses

15.4.1.1. Assessments from Binge Eating Diary

The number of binge days per week at each assessment timepoint will be derived based on clinician review of the binge eating diary collected in the time intervals as follows:

- Baseline: binge eating diary completed for 14 consecutive days immediately prior to the Baseline visit and starting no sooner than the day after the screening visit;

- Weeks 1, 2, 3, and 4 (ie, Visits 3, 4, 5, and 6): binge eating diary collected at each visit, which will span from the previous visit to the current visit and therefore cover Weeks 1, 2, 3, and 4, respectively;
- Weeks 6, 8, 10 and 12 (ie, Visits 7, 8, 9, and 10): binge eating diary collected at each visit, which will span from the previous visit to the current visit and therefore cover Weeks 5/6, 7/8, 9/10, and 11/12, respectively.

Specifically, the number of binge eating days per week at baseline is calculated as the number of binge eating days in the 14 days immediately prior to the Baseline visit multiplied by 7 and divided by the number of days in the Baseline period (ie, 14 days); the number of binge days per week in a visit that spans between 2 scheduled visits is calculated as (total number of binge days) x 7 / (total number of assessed days in the visit span). If missing diary entries exist during an assessed period for a subject, the available non-missing diaries from the subject will be used to derive the number of binge days per week adjusted by the number of non-missing diary days accordingly.

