3.1. Determination of Sample Size

The sample size for this study was estimated based on 2 hypotheses associated with the primary efficacy endpoint (change from baseline in number of binge days per week at Week 12). A fixed sequence closed testing procedure was used to adjust for 2 comparisons of dasotraline doses vs placebo (ie, with dasotraline 6 mg vs placebo tested first and dasotraline 4 mg vs placebo tested after if the previous one is significant at the 0.05 level) for the sample size justification. Based on the Study SEP360-221 results, assuming a common standard deviation (SD) of 1.75 and a mean improvement of 0.9 (effect size 0.517) and 0.8 (effect size 0.457) over placebo for change from baseline in number of binge days per week at Week 12 for dasotraline 6 mg/day and 4 mg/day doses respectively, a sample size of 96 subjects per treatment group will provide at least 85% conjunctive power to reject both null hypotheses. An upward adjustment of approximately 40% is assumed to compensate for subjects who are randomized but discontinued from the study, thus, a total sample of 480 subjects (160 subjects per group) will be randomized with a ratio of 1:1:1 for placebo, and dasotraline 4 mg/day and 6 mg/day. The sample size calculation was based on Monte Carlo simulation from EAST 6.4.

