5.1. Efficacy Variables

5.1.1. Variables Derived Per Binge Eating Diary

All binge episodes will be captured daily by the subject in a binge eating diary using paper format to record the date, duration (total hours of binging), type of binge episode (meal or non-meal), amount and type of food, and number of binges. The number of binge days per week and the number of binge episodes per week at each assessment timepoint will be derived based on clinician review of the binge eating diary collected in the time intervals as follow:

- Baseline: binge eating diary completed for 14 consecutive days immediately prior to the Baseline visit;
- Weeks 1, 2, 3, and 4 (ie, Visits 3, 4, 5, and 6): binge eating diary collected at each visit, which will span from the previous visit to the current visit and therefore cover Weeks 1, 2, 3, and 4, respectively; Particularly, Week 1 visit period will span from Day 1 (ie, 1st dose day) to one day before Week 1 visit date (inclusive).
- Weeks 6, 8, 10 and 12 (ie, Visits 7, 8, 9, and 10): binge eating diary collected at each visit, which will span from the previous visit to the current visit and therefore cover Weeks 5/6, 7/8, 9/10, and 11/12, respectively.
- Withdrawal Weeks 1, 2, 3 (ie, Week 13, 14, and 15): binge eating diary collected at each withdrawal visit, which will span from the previous visit to the current visit and therefore cover Visits 11, 12, and 13, respectively.

Specifically, the diary information collected on the post-DB baseline visits will be counted into the corresponding week span; for an example, diary collected on Week 1 visit data will be counted into the diary data at Week 1; diary collected on Week 2 visit data will be counted into the diary data at Week 2; and so on.

Diary records reviewed at early termination visit will be mapped into scheduled visit. Mapping rule of early terminated visit for binge eating diary based on study day is provided in [Section 6.1.4.1](#).

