Table 5: Visit Window for Early Termination Visit in Treatment Period for Binge Eating Diary Data

Last Scheduled Visit	Time Interval (Day) ^a	Analysis Visit (label on output)
Baseline *	DLSV – DLSV+30	Week 1
Week 1	DLSV – DLSV+30	Week 2
Week 2	DLSV – DLSV+30	Week 3
Week 3	DLSV – DLSV+30	Week 4
Week 4	DLSV – DLSV+40	Week 6

321

Week 6	DLSV – DLSV+40	Week 8
Week 8	DLSV – DLSV+40	Week 10
Week 10	DLSV – DLSV+40	Week 12
^a Relative to the day of the first dose of double-blind study medication DLSV=study day of last scheduled visit relative to the first dose of study medication *: for the study day of the ET visit > Day 1		

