6.2. Methods of Analysis

6.2.1 General Methodology

All statistical inference analyses will be performed with 2-sided tests at a significance level of 0.05, and 2-sided 95% confidence intervals (CIs) will be calculated whenever appropriate. All

321

data will be summarized by treatment group and visit as appropriate. All subject data will be presented in data listings by subject.

Data for unscheduled assessments will be included when deriving baseline values and the worst case analysis during an assessed period. Unscheduled visits will also be included in treatment endpoint (Week 12 LOCF), which is the last available non-missing treatment endpoint carried forward to Week 12.

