The proportion of binge eating responders at Week 12 will be analyzed using a logistic regression model and LOCF approach with factors of treatment, pooled center, baseline binge days category (stratification factor), and baseline number of binge episodes per week as covariate. For subjects who are discontinued, binge eating responders at Week 12 LOCF is defined per the last post-baseline time period during the treatment period that binge diary is assessed. To ensure that the logistic regression model is feasible, pooled region may be removed from the analysis model if some pooled center has no responder either because there is a small number of subjects in the pooled center or subjects experience little change (for example, no subject achieving at least 75% reduction in number of binge episodes per week). In addition, for each dasotraline group (vs. Placebo), effect size and the number needed to treat (NNT) will be presented as well. The effect size will be calculated as $\log(\text{odds ratio}) \cdot \sqrt{3}/\pi$, where odds ratio is based on 2 by 2 contingency table and the NNT is derived as $1/\text{Risk Reduction}$, where Risk Reduction (RR) = (each dasotraline response rate – placebo response rate). The 95% CI of NNT will be obtained similarly by using the 95% CI of the RR when both lower and upper confidence limits are positive. The NNT and 95% CI results will be provided in whole number format as any fractional values are rounded up to the nearest whole number (the lower confidence limit is rounded down and the upper confidence limit is rounded up.)

As a supportive analysis, the proportion of binge eating responders for achieving 75% reduction over time will be analyzed, respectively, by an inverse probability weighting (IPW) Generalized Estimating Equations (GEE) model. See [Attachment 9.3.4 \(\[6\]\)](#) for details.

321

In addition, the number and percentage of subjects in the following categories for reduction in the number of binge eating episodes from baseline will be summarized by treatment and by visit:

- cessation (defined as 100% reduction)
- 99% to 75% reduction
- 74% to 50% reduction
- other

At each assessment time point, for each of above continuous secondary efficacy variables, summary statistics (N, mean, standard deviation, median, and range) will be presented for the actual values and the changes from baseline. The 95% CIs of the changes from baseline will also be presented.

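### An early-termination diary span has no minimum length, so a single diary day can become a visit value of 0 or 7 binge days/week and can decide a dropout's LOCF responder status

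*SAP*

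**What the plan says.** SAP 5.1.1 provides that "Diary records reviewed at early termination visit will be mapped into scheduled visit". The mapping is in SAP 6.1.4.1, Table 5 ("Visit Window for Early Termination Visit in Treatment Period for Binge Eating Diary Data"). There the early-termination (ET) span runs from the study day of the last scheduled visit (DLSV) to DLSV+30 or DLSV+40 and takes the label of the next scheduled visit. Last visit Week 10 becomes Week 12. The table has an upper bound but no minimum length.

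SAP 5.1.1.1 defines assessed days as current visit day minus previous visit day, reduced to days with a non-missing diary. SAP 5.1.1.2 and protocol 15.4.1.1 give the weekly value as ("total number of binge days) x 7 / (total number of assessed days in the visit span"). Neither states a minimum.

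The visit values are the response in the primary ITT MMRM (SAP 7.2.3.2.1), which has no term for assessed days. For the ≥75% responder endpoint, SAP 7.2.6.2 says: "For subjects who are discontinued, binge eating responders at Week 12 LOCF is defined per the last post-baseline time period during the treatment period" in which the diary was assessed, whatever its length. Protocol 15.4.1.5 has the same rule.

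SAP 7.2.3.2.4 acknowledges that assessed days differ between subjects, early dropout being one cause. It answers with a binomial GLMM that is run only if the primary model's assumptions appear to fail.

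**The concern.** A subject who attends Week 10 and terminates the next day contributes one diary day. Scaled to a week it can only be 0 or 7, yet it enters the MMRM as an observed Week 12 value alongside values built on about 14 days. After an earlier last visit the value takes an earlier label, still enters the MMRM, and is carried to Week 12 in the LOCF ANCOVA.

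The responder endpoint is more exposed because it has a threshold. One binge-free day is a 100% reduction, so a dropout whose binge frequency has not changed can be counted as a responder by chance. The design allows for about 40% discontinuation (SAP 3.1), and protocol 13.3 asks for the EOT visit as soon as possible after stopping, so irregular short spans should be expected.

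Other rules in the plan do not reach these analyses. The exclusions in SAP 7.1.6 for more than 5% missing diary or under 28 days of exposure act only on the PP set, and a completed one-day span has no missing entry. The 28-day completeness rule in SAP 5.1.1.4 protects only 4-week cessation.

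**Working it through.** **The plan's own figure.** SAP 3.1 plans by "assuming a common standard deviation (SD) of 1.75 and a mean improvement of 0.9 (effect size 0.517) and 0.8 (effect size 0.457) over placebo", and says that "a sample size of 96 subjects per treatment group will provide at least 85% conjunctive power to reject both null hypotheses". With two-sided α = 0.05 (SAP 6.2.1), z = difference / (1.75 × √(2/96)). Marginal power is 94.6% for 6 mg and 88.6% for 4 mg. Treating the two statistics as bivariate normal with correlation 0.5 (shared placebo arm), conjunctive power is 85.4%; a t-test simulation gives 85.2%. Also 96/(1 − 0.40) = 160. The figures reproduce and are not in dispute. The SD of 1.75 serves below as a yardstick.

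**One-day span.** ET at DLSV+1 gives 1 assessed day, so the value is 0 × 7/1 = 0 or 1 × 7/1 = 7. From a baseline of 5/week the change is −5 or +2, which is −5/1.75 = −2.9 or 2/1.75 = +1.1 planning SDs. At Table 5's own lower bound (ET on the DLSV day) assessed days are 0 and the formula is 0/0.

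**Sampling noise.** With independent days and daily probability p, the SD of the weekly value over k days is 7 × √(p(1 − p)/k). At a true 2 days/week (p = 2/7) this is √(10/k): 3.16 for k = 1 and 0.85 for k = 14. The expected value is 7p at every k, so under a constant rate there is noise but no bias.

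**False response.** Assume independent days, one episode per binge day and no change from baseline b, so p = b/7. The subject is a responder if count × 7/k ≤ 0.25 × b. Binomial probabilities:

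| Assessed days | b = 3 | b = 4 | b = 5 |
|---|---|---|---|
| 1 | 57.1% | 42.9% | 28.6% |
| 2 | 32.7% | 18.4% | 8.2% |
| 3 | 18.7% | 7.9% | 2.3% |
| 4 | 10.7% | 3.4% | 0.7% |
| 7 | 2.0% | 2.7% | 0.3% |
| 14 | 0.5% | 0.1% | <0.1% |

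If ET spans were uniform over 1 to 14 days, the averages would be 10.0%, 5.7% and 2.9%.

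**Size in the primary analysis (illustration).** Assume 40% dropout spread evenly over 12 weeks. Then 64 × 2/12 = 10.7 subjects per arm leave after Week 10, which is 10.7/(96 + 10.7) = 10% of Week 12 values. With spans uniform over 1 to 14 days at a true 2 days/week, the mean of 10/k is 2.32, against 10/14 = 0.71 for a full span: an excess of 1.61. Week 12 variance rises by 0.10 × 1.61/1.75² = 5%, and the standard error by about 2.6%.

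**Size in the responder comparison (illustration).** Take a 10-point difference in dropout between arms, every dropout unchanged, and 3% to 10% false response. The responder difference moves by 0.3 to 1.0 percentage points.

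**The case against.** The strongest reply is that the SAP has seen the issue. Homoscedasticity is checked with residual plots (SAP 7.2.3.2.2), and a deviation triggers a permutation test and a binomial GLMM, which weights each span by its days. This stands in part. The GLMM is the right tool, but it is conditional on a graphical judgement and does not extend to responders. The inverse-probability-weighted GEE planned for responders is not described as weighting by span length.

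A reader might infer that the rule biases the primary treatment comparison. The documents do not support that. The weekly value is unbiased at any span length under a constant rate, a one-day value errs in either direction, and the Week 12 label needs Week 10 as the last visit.

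A reader might also infer that the responder result would be materially tilted towards one arm. That would need differential dropout or differential span lengths, and the documents give neither. The endpoint is also outside the error-controlled sequence (SAP 6.2.5), and the key secondary diary endpoint already requires 28 complete days.

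Nor is the 14-day span the only fair comparator. Scheduled spans through Week 4 are about 7 days, where false response is already 0.3% to 2.7% at the baselines shown.

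**Conclusion.** The gap is real and should be closed. The derivation as written turns spans of one to three days into full visit values and lets them decide responder status. In the primary MMRM the cost is precision: about 5% more Week 12 variance under the assumed dropout pattern, with no fixed direction. In the LOCF responder endpoint the short-span error favours response: 43%, 18% and 8% for one, two and three days at a baseline of 4 days/week, against 2.7% for seven days and 0.1% for fourteen. The likely shift in the arm difference is a percentage point or less under the illustration above.

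These figures rest on independent days, one episode per binge day and no change from baseline. The distribution of ET span lengths is not in the documents, so the effect on the final estimates cannot be computed. The SAP attachments, including the one on the GLMM, are not in the available text, but the derivation sections do not refer to them for a minimum.

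**What to change.** Before database lock, amend SAP 5.1.1 and Table 5 along these lines:

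- If an ET span has fewer than a prespecified minimum of assessed days (for example 4), pool its days with the preceding post-baseline span. The pooled rate becomes that visit's value and the last value for both LOCF analyses. No value is created for the next visit.
- If the last scheduled visit is Baseline, do not pool with the baseline diary. That would mix on-treatment days into baseline and remove the subject's only diary change score. Keep the available post-baseline days as the Week 1 value and flag it.
- Run the binomial GLMM unconditionally as a sensitivity analysis.
- List the change in SAP section 4, which now declares none, as a departure from protocol 15.4.1.1 and 15.4.1.5.

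A minimum of 4 rather than 7 keeps ET spans in line with on-time scheduled spans: Week 1 runs from Day 1 to the day before the visit, so a Day 7 visit yields only 6 days. At a baseline of 4/week, a one-day span pooled with a 7-day span gives 8 days and a false-response chance of (3/7)^8 + 8 × (4/7) × (3/7)^7 = 1.3%, against 43% unpooled.

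The cost is SAP wording and a derivation change. No diary day is discarded. A few dropouts lose a noisy extra visit value, and the protocol's visit-to-visit span definition is modified for them.

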For very rare situations, a subject might miss a scheduled visit and come back at the next scheduled visit. For such a case, diary records are expected to be collected continuously without interruption. The collected diary will be reviewed on the next scheduled visit. During the double-blind treatment period, if a diary contains binge eating diary records for a missed visit, the diary records will be split into two parts by using the target day of the missed visit (see Table 2 in study protocol) as a data cut: part 1 starts from the previous scheduled visit date (inclusive)

321

to the target day of the missed visit (exclusive), and part 2 starts from the target day of the missed visit (inclusive) to the current visit (exclusive). Part 1 and Part 2 data will be used to derive binge diary related variables for previous scheduled visit and the missed visit, respectively.

5.1.1.1. Number of Binge Days, Number of Binge Episodes, and Number of Assessed Days During a Visit Period

Number of assessed days at baseline will be 14 days. The number of binge eating days per week at baseline is calculated as the number of binge eating days in the 14 days immediately prior to the Baseline visit multiplied by 7 and divided by the number of days in the Baseline period. No missing diary entry is expected. In case there is a missing diary, the non-missing diary days in 14 days immediately before randomization will be used to derive these variables.

For each post-baseline assessment visit defined in [Section 5.1.1](#),

- Number of assessed days within the visit period is defined as the difference in study day between the current visit and the previous visit (ie, study day of current visit – study day of previous visit). If missing diary entries exist during the assessed period for a subject, the number of assessed days will be derived based on the days with non-missing diaries.
- Number of binge days is counted as the binge days that occur between the previous visit date (inclusive) and a day before the current visit date (inclusive).
- Number of binge episodes is counted in a similar way. If missing diary entries exist during the assessed period for a subject, number of binge days and number of binge episodes will be derived based on the days with non-missing diaries.

5.1.1.2. Number of Binge Days per Week and Number of Binge Episodes per Week for a Visit Period

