6.1.11.3 Composite Score

Unless otherwise specified, any individual missing item in any scale won’t be imputed. When calculating a total score, subscale score, composite score, or any assessment with more than one item (e.g. Y-BOCS-BE total score and 2 subscale scores, EDE-Q global score and 4 subscale scores, EDE-QM global score and 3 subscale scores, SDS total score and 3 subscale scores, MADRS total score, HAM-A total score, CSSA total score, DESS total score), if one or more items are missing at a visit, then the associated score (ie, total score or subscale score) will be set to missing.

In the event of missing data at Week 12 for efficacy variables, the last post-baseline observation carried forward (LOCF) approach is used to impute missing values in the ITT LOCF efficacy analyses. Unscheduled visits are included in the imputation.

For analyses of the change from baseline for a given efficacy parameter, only subjects who have both baseline and at least one post-baseline measurement are included.

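### The SAP's missed-visit diary rule labels both diary segments one visit too early; followed literally, a subject who misses Week 10 but attends Week 12 has no Week 12 primary-endpoint value.

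*SAP*

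**What the plan says.** The general rule is stated several times and always the same way: a diary span takes the label of the visit that ends it.

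- SAP 5.1.1, for the two-weekly visits: diary "which will span from the previous visit to the current visit and therefore cover Weeks 5/6, 7/8, 9/10, and 11/12, respectively".
- SAP 5.1.1, by example: "diary collected on Week 2 visit data will be counted into the diary data at Week 2; and so on".
- SAP 5.1.1.1, for counting: "the binge days that occur between the previous visit date (inclusive) and a day before the current visit date (inclusive)".
- Protocol 15.4.1.1: "binge eating diary collected at each visit, which will span from the previous visit to the current visit". The protocol has no missed-visit rule.
- Baseline has its own definition in SAP 5.1.1: "binge eating diary completed for 14 consecutive days immediately prior to the Baseline visit".

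SAP 5.1.1 then covers a subject who misses one scheduled visit and returns at the next. The diary brought to the later visit is split at the missed visit's target day. Part 1 runs from the previous scheduled visit up to, but not including, that target day. Part 2 runs from the target day up to, but not including, the current visit. The paragraph closes: "Part 1 and Part 2 data will be used to derive binge diary related variables for previous scheduled visit and the missed visit, respectively".

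**The concern.** The closing sentence reverses the SAP's own convention. Part 1 ends at the missed visit, so under the general rule it is the missed visit's data. Part 2 ends at the current visit, so it is the current visit's data. The sentence gives Part 1 to the visit before the missed one and Part 2 to the missed one.

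The paragraph uses previous scheduled visit, missed visit and current visit as three separate terms, and the previous scheduled visit date is the start of Part 1. It therefore cannot be read as meaning the visit that closes Part 1.

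The case that matters most is a missed Week 10. The primary endpoint is the change from baseline at Week 12 (SAP 7.2.3.1), and the primary MMRM uses the visit-labelled values (SAP 7.2.3.2.1). If the sentence is programmed as written, a Week 12 outcome that was observed enters the model as missing, and the Week 12 period enters as Week 10.

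The supportive ANCOVA behaves differently. Under SAP 6.1.11.3 "the last post-baseline observation carried forward (LOCF) approach is used to impute missing values in the ITT LOCF efficacy analyses", so the value labelled Week 10, which is really Days 70-83, would be carried to Week 12. The primary and supportive analyses would then use different Week 12 data for the same subject.

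**Working it through.** **Inputs.** Target days from the schedule of assessments (protocol Table 2): Week 6 = Day 42, Week 8 = Day 56 (±3), Week 10 = Day 70 (±3), Week 12 = Day 84 (±1). Span rule from SAP 5.1.1.1: previous visit day to current visit day minus 1. Split rule from the missed-visit paragraph of SAP 5.1.1.

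**Step 1: reproduce the plan's own coverage with no missed visit.** On target days the general rule gives Week 8 = Days 42-55, Week 10 = Days 56-69 and Week 12 = Days 70-83. Each is 14 days and agrees with the stated coverage of Weeks 7/8, 9/10 and 11/12.

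**Step 2: Week 10 missed, Week 12 attended.** Part 1 = Days 56 to 69 (70 - 56 = 14 days). Part 2 = Days 70 to 83 (84 - 70 = 14 days).

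| Analysis visit | Sentence as written | General rule |
|---|---|---|
| Week 8 | Days 42-55 (its own span) and also Days 56-69 | Days 42-55 |
| Week 10 | Days 70-83 | Days 56-69 |
| Week 12 | no days | Days 70-83 |

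The SAP does not say whether the extra segment replaces Week 8's own span, is pooled with it or is ignored.

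**Step 3: other missed visits.** The same shift occurs each time, and the next attended visit is left empty:

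- Week 1 missed: Week 2 empty
- Week 2 missed: Week 3 empty
- Week 3 missed: Week 4 empty
- Week 4 missed: Week 6 empty
- Week 6 missed: Week 8 empty
- Week 8 missed: Week 10 empty
- Week 10 missed: Week 12 empty

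Only the last removes the primary value. For a missed Week 1, Part 1 (on-treatment Days 1-6) would be labelled Baseline, which contradicts the pre-visit Baseline definition.

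**Step 4: is the rule repaired elsewhere?** SAP Table 5 remaps diary data for early-termination visits only. No other section covers a missed visit followed by an attended one. The 4-week cessation endpoint (SAP 5.1.1.4) takes the last 28 days by date and is not affected.

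**Step 5: does the corrected label always work?** With Week 8 attended on Days 53-59 and Week 12 on Days 83-85, Part 1 is 70 - 59 = 11 to 70 - 53 = 17 days, and Part 2 is 83 - 70 = 13 to 85 - 70 = 15 days. A Week 12 value can be derived in every case, provided the diary was kept.

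**Step 6: upper bound on the power cost.** The sample-size section (protocol 15.1, SAP 3.1) gives SD 1.75, differences of 0.9 and 0.8, and 96 evaluable subjects per arm for at least 85% conjunctive power. The standard error is 1.75 × √(2/n). The two test statistics share the placebo arm, so their correlation is 0.5. Conjunctive power is the bivariate normal probability that both exceed 1.96.

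- n = 96: standard error 0.2526, expected statistics 3.563 and 3.167, conjunctive power 0.854. This reproduces the plan's claim.
- n = 96 × 0.99 = 95.04: 0.850.
- n = 96 × 0.95 = 91.2: 0.833.

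The 1% and 5% rates are assumptions, because the documents give none. The calculation also drops the affected subjects entirely, whereas the MMRM would keep their other visits.

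**The case against.** The strongest reply is that this is a slip in one sentence and that the rest of the SAP makes the intention clear. The sentence does not say that the current visit receives nothing. The general rules still apply to every post-baseline visit, so a programmer could derive Week 12 from the diary reviewed at Week 12. If the Baseline definition is allowed to override the sentence when Week 1 is missed, the Week 11/12 definition should override it when Week 10 is missed. The situation is also described as very rare. Even under the literal reading, the LOCF analyses end up with the right days at Week 12.

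Much of this stands. It is probably a wording slip, and the absurd result for a missed Week 1 supports that view. The loss of Week 12 depends on following the sentence literally. The LOCF value at Week 12 does come from the correct period, and the fate of Week 8's own span is not settled by the text. A 5% rate for this single pattern fits poorly with very rare.

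The conflict itself remains. The general rule does not override the sentence; it only shows that two rules disagree. The missed-visit rule is the specific one, and it disposes of the whole diary collected. If the general rule were applied to Week 12 as well, the text would leave open whether the span starts at Day 56 or Day 70. A programmer who follows the sentence mislabels the data. One who corrects it silently departs from the SAP. Two independent programmers could reach different Week 12 values for the same subject.

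**Conclusion.** The point holds. The missed-visit sentence contradicts SAP 5.1.1, SAP 5.1.1.1 and protocol 15.4.1.1 and is wrong as written. For each subject who misses Week 10 and attends Week 12, the literal rule puts 14 observed diary days (70-83, on target days) under the wrong visit and leaves Week 12 with none.

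At trial level the effect should be small. Only that one pattern removes the primary value. Under the assumed 1% and 5% rates, power falls by at most 0.4 and 2.1 percentage points (0.854 to 0.850 and 0.833). The rule is the same in all arms, and no bias in either direction is claimed. It should still be corrected, because the sentence decides whether some subjects have a primary-endpoint value, and a correction after unblinding would be a post hoc change to a primary derivation.

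**What to change.** Reword the end of the sentence so that Part 1 supplies the diary variables for the missed visit and Part 2 supplies those for the current visit. Leave the split at the missed visit's target day as it is. This restores the SAP's own convention, leaves Baseline with its 14 pre-visit days, and needs no additional Baseline rule.

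The cost is one SAP sentence and the matching derivation code, changed before database lock. No further data are needed.
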